Name: [name], University Hospital Sout	hampton NHS Foundation Trust
Chief Investigator:	
Signature:	Date:05/.09/.2024
[name]	
Name: [name], Professor of Musc in Rheumatology within Medicine at the University of	, ,,
Statisticians:	
Signature:	Date:23/09/.2024
[name].	
Name: [name], Professorial Fellow in University of Southampton.	Medical Statistics within the Faculty of Medicine,
Signature:	Date: .23/.09/2024
[name]	
Name: [name], Principal Research Fellow of F	
Southampton Health Technology Assessments Centr	e, University of Southampton

2 of 21

Table of Contents

1	Title Page	1
2	Signature Page	2
Tab	ole of Contents	3
List	of Abbreviations	3
Sur	nmary Information:	4
3	Background	5
4	Identification and description of the investigation and clinical device	5
5	Justification for the design of the clinical investigation	7
6	Risks and benefits of the investigational device and clinical investigation	7
7	Objectives and hypotheses of the clinical investigation	8
8	Design of the trial investigation	9
9	Trial Participants	10
10	Study Procedures	11
11	Monitoring plan	12
12	Statistical Design and analysis	13
13	Data Management	15
14	Amendments to the CIP	15
15	Deviations from clinical investigation plan	16
16	Device accountability	16
17	Statements of compliance	16
18	Informed consent process	17
19	Adverse events, adverse device effects, and device deficiencies	18
20	Suspension or premature termination of the clinical investigation	20
21	Publication policy	20
22	Bibliography	21

List of Abbreviations

AE	Adverse Event			
CI:	Chief Investigator			
LCD:	Liquid Crystal Display			
LED:	Light Emitting Diode			
ModRUM:	Modular Resource Use Measure			
OA:	Osteoarthritis			
OKS:	Oxford Knee Score			
OLED:	Organic Light Emitting			
RCT:	Randomised Controlled Trial			
TENS:	Transcutaneous Electrical Nerve Stimulation			
VAS:	Visual Analog Scale			
WOMAC:	The Western Ontario and McMaster Universities Arthritis Index			

Summary Information:

Full title Efficacy of electronic textile based transcutaneous nerve stimulation (TENS patients with knee pain due to osteoarthritis: a pilot randomised controlled				
Short title	E-Textile TENS			
Sponsor	University Hospital Southampton NHS Foundation Trust (UHSFT)			
Sponsor Ref No	RHM RHE0001			
Chief Investigator	[name]			
Funder	Medical Research Council			
Funder Ref No	MR/W029421/1			
REC No	24/SC/358 IRAS ID:335669			
Project Type	Clinical Validation Study (Observational Cohort)			
Primary Objective	To assess the efficacy of the new wearable TENS device to reduce OA knee pain and further confirm the usability of the device at home.			
Secondary Objectives	Changes in functional outcomes observed in the intervention group (TENS arm) and control group (Sham arm), Effect of using the knee wearable sleeve on knee function, health care utilisation, usability of the prototype at home over a 12 week period			
Rationale	Osteoarthritis (OA) is the most common musculoskeletal condition, with painful knee OA being highly prevalent. While people with knee OA who exercise regularly experience less pain and improved physical function, pain typically reduces physical activity, which is linked to a range of adverse health events. Knee pain is traditionally managed using medication (NSAIDs/opioids), which costs the UK £195.3 million p.a.; however these medications can cause side effects.			
	TENS is a non-pharmacological treatment that may be beneficial for pain relief, reduction of stiffness, and improvement of knee joint function. Previous research studies have highlighted a possible role for TENS in the management of painful knee OA. However, methodological concerns remain about how to use this technology optimally.			
	Our research team has developed a wearable garment with two pairs of integrated TENS electrodes around the knee together with a TENS electronic control unit. Following laboratory and home usability studies we now wish to perform a pilot RCT to inform the design of a future trial by estimating the variability of pain reduction and functional outcomes of TENS use.			
Project Observational study / Superiority Trial Design/ Classification				
Study Population	Patients with diagnosed Knee Osteoarthritis			
Total No. of Sites	1 (UHSFT)			
Study Duration	9 months			

Data collection	Data on socio-demographic and clinical characteristics, pain, function, skin reaction, medication taken, use of assistive devices, and any adverse reaction will be collected as shown in Table 1. Medication use will be recorded at each time point, with indication. Adverse events will be recorded at each time point. Safety reporting will follow GCP guidance with suspected unexpected serious adverse reactions reported to the MHRA.
Number of Participants	80 = 2 cohorts of 40 (intervention and sham)
Primary endpoint To evaluate efficacy of TENs on knee pain relief we will collect data on: the V Scale, and WOMAC-pain sub-scale.	
Secondary endpoints	Secondary outcomes of the study include the Oxford Knee Score, Western Ontario and McMaster Universities Arthritis Index, EuroQol-5 Dimensions-5 Levels, Modular Resource Use Measure and a list of adverse reactions.
Statistical Methods	Summary statistics, mixed-effects linear regression models.

3 Background

Osteoarthritis (OA) is the most common musculoskeletal condition, with painful knee OA being highly prevalent. While people with knee OA who exercise regularly experience less pain and improved physical function, pain typically reduces physical activity, which is linked to a range of adverse health events. Knee pain is traditionally managed using medication (NSAIDs/opioids), which costs the UK £195.3 million p.a. [1]; however, these medications can cause side effects.

TENS is a non-pharmacological treatment that may be beneficial for pain relief, reduction of stiffness, and improvement of knee joint function. Previous research studies have highlighted a possible role for TENS in the management of painful knee OA [2-6]. However, methodological concerns remain about how to use this technology optimally [7-8].

Our research team has developed a wearable garment with two pairs of integrated TENS electrodes around the knee together with a TENS electronic control unit.

Following laboratory and home usability studies we now wish to perform a pilot RCT to inform the design of a future trial by estimating the variability of pain reduction and functional outcomes of TENS use.

A description of the device = garment, electrodes, stimulator, cables etc can be found in the Investigator Brochure – document 3, with comprehensive details in Device Details – document 7.

4 Identification and description of the investigation and clinical device

4.1 Summary description of the investigational device.

TENS is a non-invasive peripheral stimulation technique that applies a safe electrical current through electrodes which are in contact with the skin. This treatment aims to reduce knee pain and therefore improve function and quality of life in patients who have knee osteoarthritis. Existing TENS machines normally use hydrogel electrodes which have a limited lifetime of 1-4 weeks thus requiring a regular change of electrodes. The medical device to be tested in this trial uses a knee sleeve garment with integrated dry electrodes that is suitable for long term use. The garment with integrated electrodes is easy to use and more cost effective for long term use. In addition, compared to the traditional TENS units which have many stimulation programmes, the TENS unit developed in this study has one programme alternating between high and low frequencies to reduce the heterogeneity and improve pain relief while simplifying the set up required and improving ease of use.

The device consists of a single leg sleeve which wraps-around the leg and zips up with a length that covers from the hip to the mid-calf to avoid the garment riding up. This garment is constructed from single-knit, 2-way stretch jersey fabric with an elasticised cuff on the lower leg opening to stabilise the garment. The elasticated

fabric provides a tight yet comfortable fit, ensuring a good contact between the skin and electrodes. A circular printed pattern around the knee on the garment helps users to correctly align the garment to the centre of the kneecap, to facilitate correct electrode placement. The garment has been graded into a range of 7 sizes, from XS to 3XL to fit a wide range of knee sizes.

The outer part of the garment fastens with a double-ended zip which begins at the mid-calf inseam, crosses over the upper thigh and finishes at the hip, supported by an adjustable, elasticised waistband. The garment has a pocket on the side to hold the TENS electronic unit; the pocket has a small hole at the bottom to allow a wire through to connect the electronic unit to the electrodes on the garment. The electrode connector has two pairs of conductive snaps with different colours (one pair is in black and the other pair is in white); the colour coding ensures that users correctly pair the electrodes on the garment.

Comprehensive details and illustrations of the complete device are included in Device Details – document 7.

4.2 The manufacturer of the investigational device

The University of Southampton (UoS) is the legal manufacturer of the investigational device and will take on responsibility for the device itself. The project team has developed a comprehensive Quality Management System (QMS) with dedicated support from IMed, a specialist regulatory consultancy company. The device will be manufactured at UoS following the QMS to ensure device safety, function, usability, and regulatory compliance. UoS will receive parts/components from approved suppliers (e.g. Conductive Transfers Ltd for printing the conductive lamination film used in electrode manufacturing, PCBway Ltd for PCB manufacturing and population for the TENS electronic control unit) who have a demonstrated capability in manufacturing the required parts of the investigational device. For example, Conductive Transfers Ltd has supplied conductive lamination film for a medical device company (e.g. Atlantic Therapeutics) who sell an electrotherapy device for strengthening pelvic floor muscles. The electrode garment will be manufactured in the lab at UoS and the TENS electronic control unit will be assembled at UoS. Device testing will be conducted at UoS to ensure quality and the safety and functional requirements, and the requirement set in the standards (e.g. IEC 60601-1).

4.3 Model Name/number including software version and accessories, permitting full identification

Each garment will have a unique serial number. Similarly, the electronic control unit will have a unique serial number (Issue1-Electronics-001 incremented for each electronic circuit. The research team will keep a record of the electronic units and garments assigned to each participant to maintain traceability of the medical device during and after the clinical investigation. Software version is Issue 1 for the RCT and is identical for all participants.

Device constituent parts:

Garment = Issue 1; Stimulator Electronics = Issue 1; Software = Issue 1.0.0

Detachable components:

Interconnecting cable model reference: Lot1-CG-Cable

Accessories:

- USB Charging cable Model: MinTENS-RCT1-USB
- Instructions for use Model: MinTENS-RCT1-IFU
- Conductive electrode gel: MinTENS-RCT1-Gel
- Plastic Bag Model: MinTENS-RCT1-Bag

4.4 How traceability shall be achieved during and after the clinical investigation, for example, by assignment of lot numbers, batch numbers, or serial numbers.

As above. All garments and units will be labelled and details recorded on a database indicating to which participants they have been allocated. Supplier batch numbers on components will also be recorded to enable fault identification / recall as appropriate.

4.5 Intended purpose of the investigational device.

The intended purpose of this device is to reduce knee pain among individuals with knee OA. The pilot study will compare pain levels between the intervention group and the sham group. Additionally, it will further confirm the usability of the device at home.

4.6 The populations and indications for which the investigational device is intended.

The intended users are people with knee pain potentially associated with knee OA.

4.7 Description of the investigational device, including materials in contact with tissues or body fluids.

The investigational device is described earlier under 'Description of the Device. It is a garment plus an associated electronic unit coupled together using an interconnecting cable between them.

Materials in contact with the skin: The inner part of the garment will be in contact with the skin, this includes the fabric, elasticated bands, electrodes and the encapsulation layer on top of the conductive tracks. Participants will be asked to ensure the skin around their knees is clean before donning the device, and a conductive electrode gel will be applied to the electrodes.

A table detailing the composition of the materials that come in contact with skin is included in the Investigator Brochure – document 3.

4.8 Summary of the necessary training and experience needed to use the investigational device based on risk assessment.

All garments and associated electronic units will have instructions that describe how to put the garment on with illustrations and how to set up the TENS treatment (i.e., intensity of TENS and duration of the session). All instructions include safety precautions and troubleshooting.

See Instructions for Use - document 10.

4.9 Description of the specific medical or surgical procedures involved in the use of the investigational device.

There are no medical or surgical procedures involved in the use of this device.

4.10 References to the IB and IFU.

As specified in this document, further details and information as appropriate are included in the Investigator Brochure – document 3 and Instruction for Use – document 10.

5 Justification for the design of the clinical investigation

5.1 An evaluation of the results of the relevant pre-clinical testing/assessment and prior clinical investigations, carried out to justify the use of the investigational device in human subjects.

Based on results from the initial lab tests and subsequent home usability testing carried out prior to this RCT there was an average reduction in pain of 54.2%. Thus this pilot trial with further participants is justified.

5.2 An evaluation of clinical data that are relevant to the proposed clinical investigation

Literature shows TENS is effective in reducing pain as described in document 3.

5.3 A description of the clinical development stage.

This investigation is at the pre-market stage of clinical development (pilot study).

6 Risks and benefits of the investigational device and clinical investigation

6.1 Anticipated clinical benefits

Reduction in pain, stiffness, medication; improvement of knee functions and quality of life.

6.2 Anticipated adverse device effects associated with device

There are no anticipated adverse effects but there is a potential for low level side effects as described in section 7.5.

6.3 Risks associated with participation in the clinical investigation

All risks have been assessed in the risk and hazard analysis (DHF-032 and DHF-031). All other risks identified are low other than the medium risk below:

6.4 Residual risks associated with study procedures

Skin irritation may take time to disappear. This depends on the individual as to whether, or when, it occurs, and typically disappears within a few days.

6.5 Possible interactions with concomitant medical treatments

There is a theoretical risk of interference with a cardiac pacemaker - patients with implanted devices are excluded from the trial.

6.6 Steps that will be taken to control or mitigate the risks.

Participants are advised to discontinue treatment if any skin irritation occurs and consult the team.

Detailed user instructions have been developed with input from the end users. Home usability feedback has been integrated to improve the device usability. The study will be conducted following the procedure set out in the MHRA/HRA documentations.

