9.5 Point of randomisation

In person visit when the device is allocated.

9.6 Total expected duration of the clinical investigation.

12 weeks. Rolling recruitment over 5 month period, garment fabrication and fitting, 12 weeks home use, return of device. Total for study as a whole 9 months.

10 Study Procedures

10.1 Description of all the clinical investigation-related procedures that subjects undergo during the clinical investigation including any deviation from normal clinical practice.

A screening clinic visit will take place after an initial phone eligibility check to ensure that all participants have been diagnosed with knee OA according to the American College of Rheumatology criteria [13].

People who screen positive and consent to be part of the trial will be asked to attend three visits in person, complete follow-up questionnaires, and will receive a maximum of 4 phone calls over a period of approximately 3 months. The visits in person will take place in facilities within the University of Southampton, either at Winchester School of Art or Southampton General Hospital, on a mutually convenient date (daytime or exceptionally in the evenings).

In the first in person visit, a research nurse will take body measurements and will ask participants to try the standard size of TENS garment, which is closest to their measured size. After that, when the garment is ready, participants will visit the lab at Winchester School of Art to collect a garment with instructions and will receive guidance on what they need to do at home. They will be instructed to use the garment at least 5 out of the 7 days for 12 consecutive weeks. People will choose whether they prefer to undergo daily TENS in one session of 30 to 60 minutes or two separate sessions with a duration of 30 minutes each.. Participants will be given either an intervention or sham device – only the member of the research team distributing the garment at this point will be aware of which has been assigned.

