- 3. Analysis and Documentation: The returned devices will undergo analysis, and the findings will be thoroughly documented.
- 4. Stakeholder engagement: Depending on the reason to recall the device, relevant stakeholders (such as material suppliers or PCB manufacturers) will be informed of the findings. A mitigation plan will be devised and implemented.
- 5. Further investigation will occur to identify the root cause of the issue, and corrective actions will be taken to prevent similar problems in the future.

The CI or Sponsor may take urgent safety measures to ensure the safety and protection of trial participants from any immediate hazard to their health and safety. The measures may be taken without prior authorisation from the MHRA or REC. However, the CI will ensure all relevant parties (Sponsor, REC and MHRA) are notified of the changes within 3 days in writing detailing the reasons for the urgent safety measures and the plan for further action.

19.7 Details of the process for reporting device deficiencies.

Any device deficiencies observed by participants should be reported immediately to a member of the Research Team – contact details are included in IFU and on device labels.

19.8 List of foreseeable adverse events and anticipated adverse device effects, together with their likely incidence, mitigation, or treatment.

Some skin irritation is a foreseeable adverse event. Use of the device should be stopped for 24 hours in the first instance to allow for recovery. If a serious irritation arises, use of the device should be discontinued. No treatment is prescribed, but a topical lotion can be applied as appropriate. There are no other anticipated adverse device effects.

19.9 Emergency contact details for reporting serious adverse events and serious adverse device effects.

Emergency contact details are included in IFU.

19.10 Information regarding the DMC, if established.

A Data Monitoring Committee will be convened.

20 Suspension or premature termination of the clinical investigation

20.1 Criteria and arrangements for suspension or premature termination of the whole clinical investigation or of the clinical investigation in one or more investigation sites.

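### Protocol sections 6.6 and 19.8 give conflicting instructions for non-serious skin irritation, the only foreseeable adverse event that the protocol names

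*Protocol*

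**What the plan says.** Three parts of the protocol bear on what happens when a participant develops skin irritation.

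- **Section 6.6 (risk mitigation):** "Participants are advised to discontinue treatment if any skin irritation occurs and consult the team". The trigger is irritation of any degree.
- **Section 19.8 (foreseeable events):** "Some skin irritation is a foreseeable adverse event". The first action is a pause: "Use of the device should be stopped for 24 hours in the first instance to allow for recovery". A further step follows for worse cases: "If a serious irritation arises, use of the device should be discontinued". The section closes with "There are no other anticipated adverse device effects".
- **Section 6.4 (residual risks):** irritation "typically disappears within a few days".

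Section 7.5 lists minor skin irritation as a risk and then says that no adverse device effects are expected.

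On exposure, section 10.1 says of participants: "They will be instructed to use the garment at least 5 out of the 7 days for 12 consecutive weeks". Table 1 has adverse effects recorded at weeks 1, 4, 8 and 12. Phone calls at weeks 1, 4 and 8 are made only as needed.

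**The concern.** The protocol names one foreseeable adverse event and gives two instructions for it. Use is unsupervised at home, so the participant, or whoever in the team answers the phone, has to apply the rule at the time. Two people with the same mild irritation could be handled differently, depending on which section shaped the advice they were given.

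Two things are at stake:

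- **Safety handling.** Section 6.6 brings the team in at the first sign of irritation. Section 19.8 on its own does not.
- **Device exposure.** A brief pause and a discontinuation lead to very different amounts of treatment. The trial is meant to assess efficacy and to confirm that the device is usable at home, and the home-use hypothesis in section 7.4 explicitly includes safety.

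**Working it through.** No figure in the protocol depends on this point, so there is none to reproduce. The check is a comparison of the text, followed by a bound on what one participant's exposure could be.

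**Step 1. The two instructions by degree of irritation.**

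| Irritation | Section 6.6 | Section 19.8 |
|---|---|---|
| Not serious | Discontinue and consult the team | Pause for 24 hours; no mention of consulting |
| Serious | Discontinue and consult the team | Discontinue; no mention of consulting |

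The action on the device agrees in the second row and conflicts in the first. The step of consulting the team appears in only one section in both rows.

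**Step 2. Does *discontinue* in 6.6 simply mean pause?** Section 19.8 uses the same verb for the step that goes beyond a 24-hour stop. In the protocol's own usage the two actions are therefore distinct. Nothing says which section takes precedence.

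**Step 3. Is 19.8 complete enough to settle the matter alone?** It does not say what makes an irritation serious, or whether the formal definition of a serious adverse event in section 19.3 is meant. Section 6.4 expects irritation to last a few days, yet 19.8 does not say what happens when non-serious irritation is still present after 24 hours.

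**Step 4. Labelling.** Section 7.5 says that no adverse device effects are expected. The closing sentence of 19.8 says that no *other* ones are, which counts irritation as one.

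**Step 5. Exposure of one participant.** The inputs are the minimum of 5 use days per week and the 12 weeks in section 10.1.

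- Minimum planned use: 5 × 12 = 60 days.
- Under 19.8, a 24-hour stop touches at most two calendar days. The schedule leaves 7 − 5 = 2 spare days a week, so the minimum for that week could still be met.
- Under 6.6, if discontinuation is permanent (an assumption, since 6.6 does not say so), a stop at the end of week *w* forgoes 60 − 5*w* days: 55 of 60 at week 1, 40 of 60 at week 4, 20 of 60 at week 8.

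**Step 6. Time until the team learns of an episode.** If a participant follows 19.8 alone and does not call, the event surfaces at the next scheduled collection. The longest interval is 8 − 4 = 12 − 8 = 4 weeks.

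**Step 7. Trial level.** Multiplying step 5 up to an arm of 40 needs the incidence of non-serious irritation. The protocol gives none, so the calculation stops here.

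**The case against.** The best defence is that the sections can be read together: 6.6 is the summary, consulting the team implies that the team advises on what follows, and 19.8 supplies the detail. It is true that 6.6 does not say the stop is permanent. But the defence has to give one verb two meanings, and it leaves the consultation step in one section only. It also matters that participants act on the Instructions for Use, which are not shown. Whether participants actually receive conflicting advice therefore cannot be established. A separate document cannot, however, make two protocol sections agree.

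The protocol already covers much of the recording. Skin reactions and adverse events are collected, a daily-use diary is kept, section 19.6 has the research team screen any reported event, and section 12.2 presents adverse events by arm. That stands, and no new data collection is needed.

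A reader might also infer stronger points that the protocol does not support:

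- **That section 6.2 contradicts 19.8.** Its opening, "There are no anticipated adverse effects", looks like a contradiction. The sentence goes on to allow for low-level side effects and refers to 7.5, which names irritation. The labelling problem lies between 7.5 and 19.8.
- **That the 6.6 rule would use up the drop-out allowance.** The allowance is 40 × 0.125 = 5 per arm. Section 9.3.1 describes withdrawal as the participant's own choice and ends data collection only at withdrawal. Someone who stops the device can stay in follow-up and in the intention-to-treat analysis. Section 12.5.6 also continues recruitment until 70 participants have complete data, so the allowance is not a ceiling.
- **That discontinuation would differ by arm.** Sham stimulation ends after 4 minutes and active sessions run for 30 to 60 minutes, but the protocol does not link irritation to stimulation time. Section 4.7 lists fabric, bands, electrodes, encapsulation and gel as skin contacts and describes no different garment for the sham arm.

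**Conclusion.** The conflict is real, lies in the current text, and is confined to two things: what to do with the device when irritation is not serious, and whether the team is to be consulted. The inconsistent label between 7.5 and 19.8 is a smaller matter of the same kind.

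The consequences that follow from the text are inconsistent safety handling and inconsistent exposure for the one event the protocol foresees. For one participant the two rules can differ by anything from almost nothing to 55 of 60 minimum use days. The upper figure assumes a permanent stop at the end of week 1. For the trial as a whole the effect on exposure or retention has no computable size, because no incidence is given and stopping the device is not defined as withdrawal. The point should be corrected, but it is not evidence that the sample size or the analysis is unsound.

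**What to change.** The sponsor and investigator should:

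1. Reconcile sections 6.6 and 19.8 so that one instruction covers irritation of every degree. It should state whether the team is to be consulted, what counts as serious, and what follows if irritation outlasts the first pause, if a pause is kept. Which clinical rule applies is for them to decide.
2. Align section 7.5 with 19.8 on whether skin irritation is an anticipated adverse device effect.
3. Check the Instructions for Use and the participant information sheet against the reconciled text, so that every participant in both arms receives the same instruction.

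The cost is wording in the protocol and, if they differ, in the participant documents, with whatever approval those amendments need. No patients, visits, procedures or data items are added.
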